9.4.1.9 Time to death or distant metastasis

TTDM will be defined as the time from the date of randomisation until the first date of distant metastasis or death in the absence of distant metastasis. Distant metastasis is defined as any new lesion that is outside of the radiation field according to RECIST 1.1 or proven by biopsy. Participants who have not developed distant metastasis or died at the time of analysis will be censored at the time of the latest date of assessment from their last evaluable RECIST 1.1 assessment. However, if the participant has distant metastasis or dies after 2 or more missed visits, the participant will be censored at the time of the latest of the latest evaluable RECIST 1.1 assessment prior to the 2 missed visits. If the participant has no evaluable visits or does not have baseline data, they will be censored at Day 1 unless they die within 2 visits of Baseline, which then will be treated as an event with date of death as the event date.

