9.5.1.1 Primary endpoint: Progression-free survival

The primary PFS analysis will be based on the programmatically derived RECIST 1.1 using the BICR tumour assessments in the mITT. The analysis will be performed using a stratified log-rank test adjusting for the level of PD-L1 expression (PD-L1<1% or PD-L1 \ge 1%) and prior therapy (cCRT or sCRT). The effect of durvalumab versus placebo treatment will be estimated by the HR together with its corresponding 95% CI and p-value.

KM plots of PFS will be presented by treatment arm. Summaries of the number and percentage of participants experiencing a PFS event and the type of event (RECIST 1.1 or death) will be provided along with median PFS for each treatment.

Sensitivity analyses will be performed to assess possible evaluation-time bias that may be introduced if scans are not performed at the protocol-scheduled timepoints. The midpoint between the time of progression and the previous evaluable RECIST 1.1 assessment will be analysed using a log-rank test. For participants whose death was treated as PFS event, the date of death will be used to derive the PFS time used in the analysis. This approach has been shown to be robust even in highly asymmetric assessment schedules (Sun and Chen 2010).

Attrition bias will be assessed by repeating the PFS analysis except that the actual PFS event times, rather than the censored times, of participants who progressed or died in the absence of progression immediately following 2 or more non-evaluable tumour assessments will be included. In addition, participants who take subsequent therapy prior to progression or death will be censored at their last evaluable assessment prior to taking the subsequent therapy. This analysis will be supported by a KM plot of the time to censoring where the censoring indicator of the PFS analysis is reversed.

A sensitivity analysis will be performed by analysing the Investigator assessments. The stratified log-rank test will be repeated on these data. The HR and 95% CI will be presented.

If applicable, a sensitivity analysis will be performed by excluding sCRT participants with 1 concurrent chemotherapy and radiation cycle using BICR tumour data (RECIST 1.1). The stratified log-rank test will be repeated on these data. The HR and 95% CI will be presented.

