From the investigator's review of the imaging scans, the RECIST 1.1 tumour response data will be used to determine each patient's visit response according to RECIST 1.1. At each visit, patients will be programmatically assigned a RECIST 1.1 visit response of CR, PR, SD or progression of disease (PD), using the information from target lesions (TLs), non-target lesions (NTLs) and new lesions and depending on the status of their disease compared with baseline and previous assessments. If a patient has had a tumour assessment that cannot be evaluated, then the patient will be assigned a visit response of not evaluable (NE) (unless there is evidence of progression in which case the response will be assigned as PD).

RECIST 1.1 outcomes (i.e., PFS and ORR etc.) will be calculated programmatically for the BICR and site investigator data from overall visit responses.

The above derivations will be programmed for the BICR based upon RECIST 1.1 assessments. Measurements from the reviewer selected by the adjudicator will be used when adjudication for overall visit response has occurred, but in the case where no adjudication was required, the measurements from the reviewer who reviewed the baseline scan first will be used for this analysis. Note: this window rule will be applicable to other secondary efficacy outcome endpoints that involve RECIST 1.1 scans.

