3.2.2.6 Time to death or distant metastasis (TTDM)

TTDM (per RECIST 1.1 as assessed by BICR) will be defined as the time from the date of randomisation until the first date of distant metastasis or death in the absence of distant metastasis. Distant metastasis is defined as any new lesion that is outside of the radiation field according to RECIST 1.1. For this reason, the TTDM endpoint will be determined from recurrent disease that occurs outside of the structures contained within the thorax, including lymph nodes, pulmonary, pleural, and mediastinal metastatic sites and excluding the heart. The locations of distant metastases will be defined and documented prior to database lock/unblinding.

Patients who have not developed distant metastasis or died at the time of analysis will be censored at the time of the latest date of assessment from their last evaluable RECIST 1.1 assessment. However, if the patient has distant metastasis or dies after 2 or more missed visits, the patient will be censored at the time of the latest RECIST 1.1 assessment prior to the 2 missed visits. If the patient has no evaluable visits or does not have baseline data, they will be

censored at Day 1 unless they die within 2 visits of baseline, which then will be treated as an event with date of death as the event date.

3.2.2.7 **Time from randomisation to second progression or death (PFS2)**

Time from randomisation to second progression or death (PFS2) will be defined as the time from the date of randomisation to the earliest of the progression event subsequent to first subsequent therapy, or death.

There are two preconditions to have PFS2 second progression event: 1) observation of primary PFS event (first progression) by Investigator; 2) received subsequent anti-cancer therapy. The primary PFS event includes only radiological progression by RECIST 1.1, as per Investigator.

The date of second progression will be recorded by the Investigator in the eCRF and defined according to local standard clinical practice and may involve any of the following: objective radiological imaging, symptomatic progression, or death. Second progression status will be reviewed ($q8w \pm 1$ week for the first 48 weeks [relative to the date of randomisation] and then $q12w \pm 1$ week [the first progression]) following the first progression event used for the primary variable PFS and status recorded.

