A sensitivity analysis will be performed to assess possible evaluation-time bias that may be introduced if scans are not performed at the CSP-scheduled time points. The midpoint between the time of progression and the previous RECIST 1.1 assessment (using the final date of the assessment) will be analysed using a stratified log-rank test, as described for the primary analysis of PFS. Note that midpoint values resulting in non-integer values should be rounded down. For patients whose death was treated as a PFS event, the date of death will be used to derive the PFS time used in the analysis. This approach has been shown to be robust to even highly asymmetric assessment schedules ([Sun and Chen 2010](#)). To support this analysis, the mean of patient-level average inter-assessment times will be tabulated for each treatment. This approach will use the BICR data. This analysis will be repeated on the ITT set.

2. Attrition bias

Attrition bias will be assessed by repeating the PFS main analysis except that the actual PFS event times, rather than the censored times, of patients who progressed or died in the absence of progression immediately following two, or more, missed tumour assessments will be included. In addition, and within the same sensitivity analysis, patients who take subsequent therapy prior to their last RECIST 1.1 assessment or progression or death will be censored at their last assessment prior to taking the subsequent therapy.

An attrition bias sensitivity analysis will also be performed. This analysis will be a repeat of the PFS primary analysis except that the actual PFS times of the patients who missed two or more tumour assessments (rather than censored times) will be used.

The above analyses will be supported by the Kaplan-Meier plot of the time to censoring using the PFS data from the primary analysis and where the censoring indicator of the PFS analysis is reversed. Except the supportive Kaplan-Meier plot, these analyses will be repeated on the ITT set.

3. Ascertainment bias

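### Three SAP date rules drop the protocol's word *evaluable*, so as written a not-evaluable scan can set the date in two PFS sensitivity analyses and in TTDM

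*SAP*

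**What the plan says.** The two documents give different anchors for three dates.

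- **Evaluation-time midpoint.** Protocol 9.5.1.1: "The midpoint between the time of progression and the previous evaluable RECIST 1.1 assessment". SAP 4.2.1, sensitivity analysis 1: "The midpoint between the time of progression and the previous RECIST 1.1 assessment (using the final date of the assessment").
- **Censoring at subsequent therapy (attrition bias).** Under Protocol 9.5.1.1, patients "will be censored at their last evaluable assessment prior to taking the subsequent therapy". Under SAP 4.2.1, sensitivity analysis 2, they "will be censored at their last assessment prior to taking the subsequent therapy".
- **TTDM censoring after two missed visits.** Protocol 9.4.1.9 uses the "latest evaluable RECIST 1.1 assessment prior to the 2 missed visits". Under SAP 3.2.2.6 the patient "will be censored at the time of the latest RECIST 1.1 assessment prior to the 2 missed visits".

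Elsewhere the SAP keeps the qualifier: for primary PFS censoring (3.2.1), for the COVID-19 death analysis (4.2.1, sensitivity analysis 6), and for ordinary TTDM censoring in the sentence just before the TTDM rule above.

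SAP Section 6 lists two changes from the protocol: the added time-to-deterioration endpoint and the removal of biopsy from the TTDM definition. It mentions none of the three differences.

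**The concern.** In the SAP's vocabulary a scan that could not be read is still an assessment. SAP 3.1 says: "If a patient has had a tumour assessment that cannot be evaluated, then the patient will be assigned a visit response of not evaluable (NE"), and SAP 3.1.2 does the same for central review. SAP 3.2.1 adds that an NE visit does not count as missed. An unqualified reference to the last or previous assessment therefore takes in NE scans, and a programmer following the text would use them.

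An NE visit did not establish that the patient was progression-free. It is a poor lower end for a progression interval and a poor progression-free censoring date. For an affected patient the derived time can only get longer.

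The two PFS sensitivity analyses exist to test the primary result, yet their anchor would be looser than that of the analysis they test. TTDM would have two different anchors within one paragraph.

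NE scans are foreseeable in this trial: Protocol 4.2.3 warns that radiation changes may make tumour assessment difficult.

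**Working it through.** **Inputs.** Scans are every 8 weeks to week 48 and then every 12 weeks, each ±1 week (SAP 3.1 and 3.2.1). Study day is date minus randomisation date plus 1 (note to SAP Table 6), so week *w* falls on day 7*w* + 1.

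**Check of the inputs against SAP Table 6.**
- Missed-visit windows: 2×8 + 1 = 17, 2×8 + 1 + 1 = 18, 8 + 12 + 1 + 1 = 22 and 2×12 + 1 + 1 = 26 weeks.
- Day cut-offs, one week before weeks 8, 40 and 48: 57 − 7 = 50, 281 − 7 = 274 and 337 − 7 = 330.

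All agree with the table.

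**Formulas.** Let E be the last evaluable scan, N the NE scan after it, and P the scan showing progression.
- Midpoint shift, SAP minus protocol: (P + N)/2 − (P + E)/2 = (N − E)/2.
- Censoring shift, SAP minus protocol: N − E.

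**One NE visit at nominal times.**

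| | E | N | P | Protocol midpoint | SAP midpoint | Midpoint shift | Censoring shift |
|---|---|---|---|---|---|---|---|
| 8-week schedule | 57 | 113 | 169 | (57+169)/2 = 113 | (113+169)/2 = 141 | 28 days = 4 weeks | 113−57 = 56 days = 8 weeks |
| 12-week schedule | 337 | 421 | 505 | (337+505)/2 = 421 | (421+505)/2 = 463 | 42 days = 6 weeks | 421−337 = 84 days = 12 weeks |

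**Off-schedule visits.** With ±1 week at each scan, the gap N − E runs from 8 − 2 = 6 to 12 + 2 = 14 weeks. The censoring shift is then 6 to 14 weeks and the midpoint shift 3 to 7 weeks.

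**Two NE visits in a row.** The gap from E to the later NE scan is 8+8 = 16, 8+12 = 20 or 12+12 = 24 weeks. The midpoint shift is half of that: 8, 10 or 12 weeks.

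**Scale across patients.** The documents give no NE rate. Purely as an assumption, suppose 2% to 10% of the patients to whom a rule applies have an NE scan in the critical position. The average time over those patients then moves by 0.02×4 = 0.08 to 0.10×6 = 0.6 weeks for the midpoint, and by 0.02×8 = 0.16 to 0.10×12 = 1.2 weeks for censoring. This says nothing about the hazard ratio, which also depends on how affected patients fall between the arms.

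**The case against.** **The omissions may be editorial.** The attrition analysis is framed as a repeat of the main PFS analysis with named exceptions, and the main analysis censors at evaluable scans. The TTDM rule directly follows a sentence that contains the word. A program built on the main derivation might well use evaluable scans throughout. This is fair as a guess about intent. However, censoring at subsequent therapy is itself one of the named departures, so the main analysis has no such rule to inherit. In TTDM, a word present in one sentence and absent from the next reads as a difference. The midpoint rule has no such context to lean on.

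**The missed-visit note does not make NE scans valid anchors.** This stands. The sentence in SAP 3.2.1 that says an NE visit is not missed still censors at an evaluable scan. It shows that NE visits are counted as attended, not that they are meant to supply dates. The problem comes from the unqualified wording of the three rules.

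**An NE visit is not always uninformative.** This stands in part, most of all for TTDM. SAP Table 5 allows an overall NE with no new lesions recorded, and TTDM turns on new lesions outside the thorax or death. Such a visit can be real evidence against distant metastasis. The same row also covers new-lesion status that is itself not evaluable, and the protocol asks for an evaluable assessment either way.

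**The consequence is limited.** This stands. None of the three analyses is in the testing hierarchy of Protocol 9.1. The trial is double-blind with central review, and nothing in the documents suggests that NE rates differ by arm. In the 8-week example the SAP midpoint (day 141) still precedes the progression date used in the primary analysis (day 169).

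**Conclusion.** The SAP departs from the protocol in three date rules without declaring it. The departure changes derived times, always to later dates, for patients whose scan just before progression, therapy switch or visit gap is NE. For one NE visit at nominal times the size is 4 or 6 weeks for the midpoint and 8 or 12 weeks for censoring. These figures are not upper bounds, since consecutive NE scans add more.

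A reader might infer three stronger things that the documents do not support:

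- *That PFS or TTDM times are in general 4 to 12 weeks too long.* Patients without an NE scan in the critical position are unaffected, and the shift rests on a literal reading of the text. How the programs are written is not shown.
- *That the primary result is at risk.* SAP 3.2.1 keeps the qualifier for primary PFS. What is affected is two PFS sensitivity analyses and one secondary endpoint.
- *That the TTDM rule undermines a check on primary PFS.* TTDM is a separate secondary endpoint, not a sensitivity analysis.

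No effect on a hazard ratio or p-value can be stated without an NE rate by arm. The point is modest but worth correcting, because the rules as written give different dates from the protocol and the remedy is simple.

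**What to change.** Restore *evaluable* in three SAP sentences and the matching program lines:

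1. SAP 4.2.1, evaluation-time bias: take the midpoint from the previous evaluable assessment.
2. SAP 4.2.1, attrition bias: censor at the last evaluable assessment before subsequent therapy.
3. SAP 3.2.2.6: censor at the latest evaluable assessment before the two missed visits.

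The same attrition paragraph differs from the protocol in a second way that the one-word change does not cure. The SAP reinstates events after two or more *missed* assessments. Protocol 9.5.1.1 speaks of two or more *non-evaluable* ones. Reconcile the two, or declare the difference in SAP Section 6. The SAP version fits the missed-visit censoring rule in Protocol 9.4.1.2 and SAP 3.2.1, so a declaration may be enough.

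The cost is one word in three places, one phrase or a line in Section 6, and a check of the programs. If the programs already use evaluable scans, only the text changes.

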4.2.2 Secondary efficacy endpoints

4.2.2.1 Overall survival

The key secondary endpoint of OS will be analysed using a stratified log-rank test, using the same methodology as described for the primary PFS endpoint. The effect of durvalumab versus placebo will be estimated by the HR together with its corresponding (1 – alpha adjusted) % CI and p-value. Kaplan-Meier plot of OS will be presented by treatment arm.

The stratification variables in the statistical modelling will be based on the values entered into Interactive voice response system (IVRS) at randomisation, even if it is subsequently discovered that these values were incorrect. Sensitivity analysis might be performed based on the values in the eCRF page if more than 10% randomised patients have discrepancies in stratification factors between IVRS and eCRF data.

Summaries of the number and percentage of patients who have died, those still in survival follow-up, those lost to follow-up, and those who have withdrawn consent will be provided along with the median OS for each treatment.

This analysis will be repeated on the ITT set.

The assumption of proportionality will be assessed in the same way as for PFS.

Overall survival status will also be listed.

Sensitivity analyses

A sensitivity analysis for OS will examine the censoring patterns to rule out attrition bias, achieved by a Kaplan-Meier plot of time to censoring where the censoring indicator of OS is reversed.

Proportional hazards will be tested firstly by examining plots of complementary log-log (event times) vs log (time) and, if these raise concerns, by fitting a time-dependent covariate to assess the extent to which this represents random variation.

The stratified Max-combo test will be conducted as a sensitivity analysis on OS, to test for treatment differences in the case of non-proportional hazards. The same algorithm as specified in [section 4.2.1](#) for PFS will be used. This analysis will be repeated on the ITT set.

The number of patients prematurely censored will be summarised by treatment arm. A patient would be defined as prematurely censored if their survival status was not defined at the DCO.

In addition, duration of follow-up will be summarised using medians:

- In censored patients who are alive at DCO only: Time from randomisation to date of censoring (date last known to be alive) for each arm.
- In all patients: Time from randomisation to the date of death or to the date of censoring for censored patients, regardless of treatment arm.

A sensitivity analysis will be performed to account for COVID-19 deaths. This analysis is a repeat of the primary OS analysis, but patients who died and the primary or secondary cause of death is due to confirmed/suspected COVID-19 infection, or a confirmed/suspected COVID-19 infection is reported as a fatal AE, are censored at their confirmed/suspected COVID-19 infection death date.

Subgroup analyses maybe performed if there is a sufficient number of OS events (≥ 20 events [≥ 10 events in each subgroup/treatment arm]). Subgroup analyses and a forest plot will be generated comparing OS between treatments in the same way as previously specified for PFS. This analysis will be repeated on the ITT set.

Cox proportional hazards modelling will be employed to assess the effect of pre-specified covariates on the HR estimate. The result from the model with and without additional covariates will be presented as specified for PFS.

Consistency of treatment effect between stratification factors will be analysed. Interactions between treatment and stratification factors will also be tested to rule out any qualitative interaction using the approach of Gail and Simon ([Gail and Simon 1985](#)), as previously specified for PFS.

4.2.2.2 **Proportion of patients alive at 12 months (OS12) and at 24 months (OS24)**

OS24 will be summarised (using the Kaplan-Meier curve) and presented by treatment arm along with 95% CI using the log-log transformation.

OS12 will be defined as the Kaplan-Meier estimate of OS at 12 months. The same analysis as for OS24 will be produced.

These analyses will be repeated on the ITT set.
Other landmarks may be summarised as appropriate.

4.2.2.3 **Objective response rate**

The ORR will be based on the programmatically derived RECIST 1.1 using the BICR tumour data, without the need for confirmation of the first documented response. The ORR will be

compared between durvalumab versus placebo using logistic regression models adjusting for the stratification factors as in the PFS analysis.

The results of the analysis will be presented in terms of an odds ratio (an odds ratio greater than 1 will favour the durvalumab arm) together with its associated profile likelihood 95% CI and p-value (based on twice the change in log-likelihood resulting from the addition of a treatment factor to the model). ^{CCI}

The covariates in the statistical modelling will be based on the stratification values entered into IVRS at randomisation, even if it is subsequently discovered that these values were incorrect.

Summaries will be produced that present the number and percentage of patients with a tumour response (CR, PR separately and CR/PR combined).

The above analyses, and summaries, for ORR will be presented for the subset of patients with measurable disease at baseline. This analysis will be repeated on the corresponding ITT subset.

Overall visit response data will be listed for all patients.

Sensitivity analyses/summaries

The following sensitivity analyses/summaries will be performed:

1. This logistic regression analysis of ORR, and summaries described above, will be repeated using the results of the programmatically derived PFS using the site Investigator data from all scans based upon RECIST 1.1 as a sensitivity analysis to confirm the results of the primary analysis. This analysis will be presented for the subset of patients with measurable disease at baseline.

2. For each treatment arm, BoR will be summarised by n (%) for each category (CR, PR, SD, PD, NE and NED) as follows:

- For the subset of patients with measurable disease at baseline (without the requirement for confirmed response)
- For all patients (without the requirement for confirmed response)
- For the subset of patients with measurable disease at baseline with the requirement for responses of PR and CR to be confirmed

- For all patients with the requirement for response of PR and CR to be confirmed

No formal statistical analyses are planned for BoR.

4.2.2.4 **Duration of response (DoR)**

Descriptive data, including Kaplan-Meier estimates, will be provided for the DoR based on BICR assessments according to RECIST 1.1 in responding patients (i.e., median DoR and 95% CIs) by treatment arm, including the associated Kaplan-Meier curves (without any formal comparison of treatment arms or p-value attached). CIs for median duration of response will be derived based on Brookmeyer-Crowley method with log-log transformation. Those patients with who do not have an objective response recorded by BICR will be censored. The summary statistics table will be performed on patients with objective response, with and without the requirement for the first documented response to be confirmed. Kaplan-Meier curve will only be repeated for DoR without the requirement for the first documented response to be subsequently confirmed. These analyses will be repeated on the ITT set.

Descriptive data will be provided for TTR without the need for confirmation of response for patients included.

The TTR will be summarised (i.e. number of patients [%] based upon the number of responders for each cohort) by the scheduled assessment timepoint that the response was first observed. Additionally, descriptive summary statistics (i.e. minimum, maximum, median, Q1 and Q3) will also be presented. This analysis will be repeated on the ITT set.

Duration of response data will also be listed.

4.2.2.5 **Progression-free survival at 12 and 18 months**

PFS12 and PFS18 summaries and analyses will be produced as for OS24 detailed in [section 4.2.2.2](#).

These analyses will be repeated on the ITT set.

Other landmarks may be summarised as appropriate.

4.2.2.6 **Time to death or distant metastasis (TTDM)**

TTDM will be analysed using identical methods (stratified log-rank test) as outlined for the analysis of PFS and adjusting for the same set of covariates, but no subgroup analysis will be performed. Median and KM plot will be presented to support the analysis. This analysis will be repeated on the ITT set.

The sensitivity analyses outlined in [section 4.2.1](#) will not be repeated for TTDM, except for a KM plot of the time to censoring where the censoring indicator of TTDM is reversed. TTDM will be based on BICR data.

